## **14 Provisions to Monitor the Data to Ensure the Safety of Subjects**

The research does not involve more than Minimal Risk to subjects, however the study investigators will conduct a periodic review of the findings to ensure that no unanticipated events have occurred. Safety data will be evaluated monthly. The study lead will review participant transcripts to review for unanticipated events.

Additionally scientific literature was reviewed to inform the safety and conduct guidelines of the study.

## **15 Withdrawal of Subjects**

**15.3** Subjects will only be withdrawn without their consent is if it becomes clear during other study procedures that the participant in fact did not meet inclusion criteria or if they fail to follow study instructions.

**15.4** Termination or safe withdrawal is not applicable to the single session, brief, behavioral interventions that will be tested in the current study.

15.3 There are no procedures that participants could withdrawal from but collect other forms of data.

**15.4** If a subject withdraws from the study and requests that their assessment data be withdrawn this will be possible. However, once aggregated data analysis is complete, it will no longer be possible for subjects to withdraw their data for that particular analysis.

**15.5** Participants can withdraw participation at any time for any reason.

## **16 Data Management/Confidentiality**

**16.1** Data will not be transferred or shared with an external entity

**16.2** The research team is only permitted to access any source of information about the subjects through secure UNM verified tools. Such as REDCap and Powerchart.

**16.3** Identifiers will be collected including participants names, dates of birth, and medical abstracts.

**16.4** The research does require access, use, and disclosure of Protected Health Information. Protected Health Information being collected includes participant names, dates of birth, and medical abstracts.

**16.5** The data being gathered is not publicly available.

**16.6** Data includes sensitive information about the occurrence of shame experiences. We describe the procedures for managing data and protecting confidentiality below.

**16.7** A Certificate of Confidentiality will be sought immediately following UNM IRB approval.

**16.8** Many steps will be taken secure the data. All study staff will receive extensive training and monitoring in study procedures and complete required ethics trainings. For all study procedures, identifying information will be kept separate from study data. The Locator Form, Informed Consent, and Participant Information forms will be the only forms with identifying information. All participants will be assigned a unique identifier. This number will be used to identify patients on assessment and medical abstraction data. Identifying data will be stored separately from assessment and medical abstraction data. A key linking participants to their unique identifier will be kept in a password protected file that is only accessible to study staff. Hard copies of data will be kept in locked offices in locked filing cabinets at the study sites or in UNM offices. Data will be transferred from the study sites back to UNM approximately weekly. Data

transfer will involve a direct trip from the study site back to UNM in a vehicle. All electronic study data and brief intervention audio sessions will be stored on a secure, encrypted server that also requires password access. Brief intervention audio sessions will be checked for the presence of identifying information and such information will be muted or 'beeped' out before the audio sessions are accessed for the intervention fidelity and quality coding. Data will only be accessible by study staff.

**16.9** Assessment and medical record abstraction data will be coded with a unique identifier. A key linking participants to their unique identifier will be kept in a password protected file that is only accessible to study staff.

**16.10** Intervention performance evaluations are measured by the MITI instrument. A percentage of all interventions will be evaluated for quality, and regular feedback will be given to the study interventionists. Weekly meetings will take place between the study interventionists and the evaluator to facilitate communication and quality improvement

**16.11**

- We will collect demographics, age and ethnicity. We will include data gathered from each measure.
- Data will be maintained and stored on REDCap with only necessary team members given access.
- Data will be collected and stored electronically through REDCap
- Data will be stored for six years following close of the study and will then be destroyed.
- Only members of the research team will have access to data.

**16.12** Data will be collected, transmitted and stored via the internet, through use of secure software, REDCap. Data will be protected via a code to ensure participant data is not identifiable. This code will be kept in a secure file cabinet, separate from the data, with limited access via a single key controlled by the PI.

**16.13** Data will be collected by audio recording during the intervention. The purpose of this recording is to measure interventionist fidelity. The recordings will not be transcribed. All electronic study data and brief intervention audio sessions will be stored on a secure, encrypted server that also requires password access. Brief intervention audio sessions will be checked for the presence of identifying information and such information will be muted or 'beeped' out before the audio sessions are accessed for the intervention fidelity and quality coding. Data will only be accessible by study staff.

**16.14** The data will not include photographs.

**16.15** Research records and consent documents will be maintained for six years after the studies completion, following HIPAA Requirements for collecting identifiable health information.

**16.16** No minors will be included in the study.

## **17 Data and Specimen Banking**

**17.1** This study does not involve banking.

**17.2** This is not a multi-center study.

## **18 Risks to Subjects**

**18.1** Participants may experience discomfort when talking about engagement in a stigmatized behavior (shame surrounding opioid use) during intervention. In addition, potential psychological distress may also be caused by issues related to sexual health topics addressed. Lastly, inadvertent disclosure of confidential data to non-study staff could be damaging to patient's reputation. Extra care will be taken to protect information during waiting room recruitment. Researchers will make no mention of shame behaviors or screening results in the waiting room. During telephone assessments, we will encourage participants to complete the brief follow-up call in a private location and explicitly ask about ability / comfort to discuss sensitive issues prior to commencing each assessment.

**18.2** We are not aware of any procedures with unforeseeable risks.

**18.3** We are not aware of any procedures with risks to embryos or fetuses.

**18.4** We do not anticipate risks to others who are not subjects.

**18.5** Steps to ensure the confidentiality of data are described above. In the case that participants become psychologically distressed by participation in the study, referral to the clinic's behavioral health care providers is available. Additionally, participants will be given the information for the Agora Crisis Center, a free crisis hotline, which can provide further support and resources. If a participant does experience psychological distress we will follow up with them over the phone the following day to ensure they are alright.

## **19 Potential Benefits to Subjects**

**19.1** Participants involved in the study will receive a brief intervention in addition to standard care and may benefit from the effects of either. However, no proven direct health benefits will accrue to the research participants. If this research is successful, then the patients may benefit from new program developments based on the findings, but this is in the future.

## **20 Recruitment Methods**

**20.1** Recruitment methods are described extensively above. Briefly, during recruitment all patients attending the South-East Heights clinic for standard services will be approached by a research team member in the waiting or exam room. The research team member will ask the patient if they are interested in learning whether they are eligible to participate in a study. Interested patients will be given a brief self-administered screening instrument (see Screening Form) assessing inclusion criteria. Patients who do not meet inclusion criteria will be informed that they are not eligible and thanked for their willingness to be screened. Participants who do meet inclusion criteria will be informed they are eligible for participation. Patients will be informed of eligibility or ineligibility once they are in the exam room.

**20.2** Potential subjects will be individuals who are attending the clinic for regularly scheduled medical visits or for behavioral health screening. No chart review or referral process will be used to recruit participants.

**20.3** We have included a recruitment script in our submission with supplementary materials.

**21 Provisions to Protect the Privacy Interests of Subjects**

**21.1** Potential subjects will be individuals who are attending the clinic for regularly scheduled medical visits or for behavioral health screening. No chart review or referral process will be used to recruit participants. No data collected as part of the study assessment or intervention will be shared with standard care providers.

**21.2** With the exception of self-report written screening, all study procedures will take place in a private office space. In addition, measures to protect confidentiality are described above.

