## 2. Background

2.1 While the emotion of guilt entails "feeling bad" about a choice, shame involves the internalization of this emotion to a feeling of "I am bad." While both emotions likely serve an adaptive function in helping individuals to modify behaviors, because of its internalized nature, shame is also often associated with negative behavioral health outcomes, and, based on our own preliminary data, lower overall well-being. Specific to the current application, individuals who misuse substances have been found to have high levels of shame and women often experience shame during pregnancy, particularly when there is a history of sexual or other trauma. The stigma associated with drug use during pregnancy is particularly high and leads to extensive shame among affected patients.

Although it is difficult to estimate the prevalence of substance misuse during pregnancy because of the impact of shame on willingness to report accurately, available data suggests that more 5% of women report use drugs during pregnancy. Nationally, more

than ten thousand infants are born to opioid addicted mothers each year. New Mexico is among the highest with rates of pregnant opioid misuse exceeding 2.5 per 1000 deliveries. The impact of substance use on the health of pregnant women and their fetuses is a significant public health concern. Opioid use during pregnancy can lead to preterm births, poor fetal growth, longer hospital stays, and birth defects. Opioid misuse during pregnancy can also lead to neonatal abstinence syndrome (NAS). NAS is a drug withdrawal syndrome that affects opioid-exposed infants shortly after birth. NAS can lead to respiratory complications, feeding difficulties, and seizures and accounts for upwards of half of all neonatal intensive care hospital unit stays.

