#### **4. Inclusion and Exclusion Criteria**

**4.3.** 20 Milagro participants will be recruited to participate in the intervention and follow-up. Participants will be screened and consented during regular medical visits at the South-East Heights clinic and the Family and Community Medicine (FCM) Clinic at [name]. During recruitment, all patients attending the clinic for standard services will be approached by a research team member in the waiting or exam room. The research team member will ask the patient if they are interested in learning whether they are eligible to participate in a study.

**4.4.** Inclusion criteria: Study participants will be Milagro patients, engaged in medication assisted treatment, at least 18 years of age, can read and speak English, are willing to be contacted for follow-up, are not incarcerated, and are within the first or second trimester of pregnancy

4.3 We will be including pregnant women in the sample.

**4.5.** Exclusion criteria: The study will not enroll non-English speaking Milagro patients, patients with obvious cognitive impairments, or those with the inability to provide informed consent.

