## **12 Study Procedures**

**12.1** There are no collaborating sites or investigators in this project.

**12.2** The study procedures are described thoroughly below:

Recruitment: Milagro patients presenting at the Southeast Heights and FCM Clinics will be approached in the waiting room or an exam room following triage and asked if they would like to voluntarily screen for a confidential study. Patients who meet eligibility criteria will be informed about the study and their option to voluntarily participate in the study. Screening will be done through REDCap and completed screening forms will be maintained with other confidential study forms.

Consent: Informed consent will be obtained from each participant before completing any research procedures. Each participant will read a document outlining the purpose and content of the research. Participants will fully understand what is expected of them throughout the research process. Participants will be made aware of potential risks, benefits, and incentives for participating in the initial meeting as well as the follow-up. During the consent process, phone numbers and other forms of contact information will be collected to perform the follow-up data collection.

Baseline Assessment: Data will be entered directly into REDCap (Research Electronic Data Capture) software via a tablet device. REDCap is a secure, web-based application designed to support data capture for research studies providing: 1) an intuitive interface for validated data entry; 2) audit trails for tracking data manipulation and export procedures; 3) automated export procedures for seamless data downloads to common statistical packages; and 4) procedures for importing data from external sources. REDCap is secure and HIPAA compliant and available for use to all UNM HSC faculty and staff.

Baseline Assessment Questions can be found in the section on study forms. Questions are self-report and may be completed individually by participants or with the support of a study staff member. Questions will include demographic variables, including age and ethnicity. Contact and locator information will be gathered.

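### A screening form on stigmatized criteria may be completed in the waiting room, which is an avoidable privacy risk and a plausible but unquantified selection risk

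*Combined protocol and SAP*

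**What the plan says.** **Privacy.** Section 21.2: "With the exception of self-report written screening, all study procedures will take place in a private office space". Screening is the only step that this sentence exempts.

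**Place of approach.** In 20.1, patients "will be approached by a research team member in the waiting or exam room". Section 4.3 says the same. In 12.2 they "will be approached in the waiting room or an exam room following triage".

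**What the form asks.** Section 20.1: "Interested patients will be given a brief self-administered screening instrument (see Screening Form) assessing inclusion criteria". The inclusion criteria in 4.4 require a Milagro patient who is, among other things, "engaged in medication assisted treatment, at least 18 years of age, can read and speak English, are willing to be contacted for follow-up". They also cover trimester and not being incarcerated. They contain no shame item and no question on amount of drug use.

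**What the protocol says about shame.** Section 2.1 states that "it is difficult to estimate the prevalence of substance misuse during pregnancy because of the impact of shame on willingness to report accurately". The same section goes on to say that shame lowers attendance and disclosure to practitioners.

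**Safeguards.** Section 18.1: "Extra care will be taken to protect information during waiting room recruitment". It then bars researchers from speaking of shame behaviors or screening outcomes in that room. Section 20.1 has the result given in the exam room, and 25.1.2 places consent in a private exam room.

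**What depends on screening.** Under Aim 1, section 13.3 reports the number approached, the proportion agreeing to be screened, the eligibility rate and the consent rate. Under Aim 2 it reports within-group changes and effect sizes, and section 3.3 expects these to inform a larger trial.

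**The concern.** The form asks a woman to put a stigmatized status in writing, and this is the step for which the plan does not require a private room. Inadvertent disclosure is a harm that 18.1 itself names, so the privacy problem stands whatever happens to the estimates.

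The statistical problem follows from the protocol's own premise. If shame makes women less willing to disclose, a public setting could lead the more ashamed to decline the form or to deny a criterion. Two results could be affected:

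- The recorded eligibility rate (Aim 1) could be too low as a description of the clinic population.
- The enrolled women could be less representative on shame, the construct that Aim 2 studies, and the effect sizes carried into the next trial would inherit this.

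The study could not detect it. Section 12.5 first measures shame after consent, so there is no shame score for women who refuse or screen out.

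**Working it through.** **1. The plan's own recruitment figure.** Section 9.3 says that 8 percent of 250 potential subjects must be recruited in ten months. This reproduces: 20/250 = 0.08. It amounts to 20/10 = 2 women per month.

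**2. Can the form be completed in the waiting room?** Sections 4.3, 12.2 and 20.1 fix where patients are approached, not where they write. Two other statements point to the waiting room as a possible place of completion. Section 21.2 would need no exception if the form were always done in private. Section 20.1 holds the result back until the patient is in the exam room, which implies that some forms are completed earlier. So it is permitted, though not required.

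**3. Do the safeguards cover it?** The bar in 18.1 is on what researchers say. Self-administration avoids spoken answers. Neither covers being seen with the form or having it read over one's shoulder.

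**4. Would a false answer be caught?** The documents conflict. Sections 20.2 and 21.1 say that no chart review is used to recruit. The checklist in section 36 (partial waiver of consent for screening) names medical records as a source to be reviewed for screening. No text commits staff to checking the form against records.

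**5. Who is screened?** Sections 4.3 and 20.1 have every patient attending for standard services approached. Section 12.2 speaks of Milagro patients. Concealment is easier to imagine in the first case, because staff there need not know who is in the program.

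**6. Illustration for the eligibility rate.** The documents give no eligibility, refusal or misreporting rate, so every input here is assumed: 60 women who would otherwise be screened, 40 of them truly eligible, and a share *c* of the eligible lost. The 20 ineligible women are assumed to answer truthfully, and the denominator is taken as those screened.

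- No loss: 40/60 = 67%.
- All lost women misreport: they stay in the denominator, so rate = 40(1 − *c*)/60.
- All lost women refuse: they leave it, so rate = 40(1 − *c*)/(60 − 40*c*).

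| *c* | All misreport | All refuse |
|---|---|---|
| 10% | 36/60 = 60% | 36/56 = 64% |
| 20% | 32/60 = 53% | 32/52 = 62% |
| 30% | 28/60 = 47% | 28/48 = 58% |

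A mixture falls between the two columns. At *c* = 0 there is no distortion.

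**7. Illustration for baseline shame.** If the lost women score *d* SD above the rest, whose mean is *m*, the mean of all eligible women is (1 − *c*)*m* + *c*(*m* + *d*) = *m* + *cd*. The enrolled mean is then *cd* below it. With an assumed *d* = 1 this is 0.1, 0.2 or 0.3 SD for the three values of *c*. With *d* = 0 it is zero. The documents give neither *c* nor *d*.

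**The case against.** The strongest case against is that the mechanism is stretched and the plan already takes care. The statement in 2.1 concerns reporting of substance misuse for prevalence estimates, whereas the form asks about eligibility. Eligible women already attend a program for opioid-using pregnant women. Staff invite them only to learn whether they qualify for a study, and the exam room is already allowed. The Screening Form and recruitment script were not among the material available, and either may contain further privacy steps. In a single-arm pilot of 20, refusals are what a feasibility study is meant to count.

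Much of this stands. A refusal is a true result of the recruitment method used, and the proportion agreeing to be screened is not made wrong by it. The size of any effect is unknown. The link from shame to a false answer on this form is inferred, and it weakens if only Milagro patients are approached.

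What does not stand is that the safeguards close the gap. They govern speech and the giving of results, not the act of filling in the form. Attending a program is also different from writing that fact down in a shared room.

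A reader might infer that screening is the only non-private step in the study. That is true only of the wording of 21.2. For telephone follow-up, 18.1 encourages a private location but cannot guarantee one.

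**Conclusion.** The concern holds as a privacy weakness and as a plausible selection risk that is cheap to remove. Under the assumptions shown, the recorded eligibility rate would fall from 67% to between 47% and 64%. That range illustrates how the rate responds and does not estimate what will happen.

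Two stronger readings are tempting, and the documents support neither. One is that the enrolled women will have lower baseline shame and so less room to improve. No document shows that the more ashamed women in this clinic refuse or misreport, and both the direction and the size depend on assumed inputs. The other is that the Aim 1 rates are invalid. Refusals are a legitimate feasibility outcome. The narrower point is that the eligibility rate may reflect the setting as well as the population, and that as planned nobody could tell how much.

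**What to change.** - **21.2:** delete the exception for screening, and word the private space so that it includes the exam room that 25.1.2 already uses for consent.
- **4.3, 12.2 and 20.1:** state that staff may invite women in the waiting room, but that the form is completed in the exam room or another private room at the same visit. Deferring it to a later visit is not advisable. That would mean tracking women who have not consented, and could carry some past the second-trimester limit in 4.4.
- **13.3:** record the place of screening and the reasons for refusal or ineligibility, and report the Aim 1 rates with them.
- **Reconcile** the absence of chart review in 20.2 and 21.1 with the section 36 checklist, and the approach to all clinic patients in 4.3 and 20.1 with the approach to Milagro patients in 12.2.

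The cost is wording changes, a few extra fields on the screening log and slightly fewer women screened per session, because waiting time is no longer used for the form. Against a need of two enrolments a month, that looks affordable, although the documents do not say how many of the 250 meet the criteria at any one time.
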